7.2 PLANNED ANALYSES

7.2.1 General considerations

There will be 3 main patient populations in this trial for analyses: the randomized set (RS), the safety set (SAF), and the per-protocol set (PPS).

Randomized Set

This patient set includes all randomized patients. Treatment assignment will be as randomized. This is the main analysis set for presentation of efficacy.

Safety Set

This patient set includes all patients who were randomized and received at least one dose of study drug. It will be the main analysis set for presentation of safety. Patients will be analyzed according to the actual treatment.

Per-Protocol Set

This patient set includes all patients in the RS who adhered to the CTP without any IPVs (potentially affecting the study outcome) which lead to exclusion from the PPS. This set will be used for sensitivity analysis on the primary and key secondary efficacy endpoints which are included in the testing hierarchy.

Important violations of the protocol will include violations of the key inclusion and exclusion criteria, incorrect medications taken, concomitant use of restricted medications, and any other violations of the protocol deemed important by the study team. All decisions concerning important protocol violations will be made prior to un-blinding of the database for the primary trial analysis.

Standard statistical parameters (number of non-missing values, mean, standard deviation (SD), median, quartiles, minimum and maximum) or frequency tables (including patient frequencies and percentages) will be calculated where appropriate.

A Clinical Trial Report will be prepared for the primary analysis.

7.2.2 Primary endpoint analyses

The time to first GPP flare up to week 48, defined by an increase in GPPGA score from baseline by ≥ 2 and a GPPGA pustulation subscore ≥ 2 , is the primary endpoint of this trial. Any use of rescue medication (see [Section 3.1](#)) or investigator-prescribed SoC prior to the first onset of a GPP flare is considered to indicate the onset of such a flare.

Primary Objective: Dose Finding

The primary analysis for the primary objective consists of a MCPMod-based testing (with respect to a non-flat dose response curve). MCPMod (multiple comparison and modelling

techniques) [R10-1424] is used to evaluate several possible dose response models (patterns), and to identify the best-fitting model or subset of models (while keeping full control of the type I error at 0.05, one-sided).

The generalized MCPMod procedure for time to event endpoints (Pinheiro et al. 2014 [R15-4293]) is based on the log hazard ratio of the active doses vs. placebo obtained via a Cox regression model on the time to first GPP flare. In detail the hazard function for patient i in stratum m (systemic concomitant use of GPP medications at randomization (yes or no)) is assumed to have the form

$$\Lambda_i(t) = \lambda_{m0}(t)\exp(\beta_1 X_{1i} + \beta_2 X_{2i} + \beta_3 X_{3i})$$

where

- $\Lambda_i(t)$ is the hazard for patient i at time t
- $\lambda_{m0}(t)$ is the unspecified, non-negative, baseline hazard function that is assumed to be the same for all subjects in stratum m
- X_1, X_2, X_3 are indicator variables representing the treatment group with $X_{ki} = 1$ if patient belongs to the active treatment group i and 0 otherwise
- $\exp(\beta_k)$ with $k=1,2,3$ is the respective hazard ratio for the 3 active treatment groups

The MCPMod test is based on the estimated log hazard rates β_k ($k=1, 2, 3$) as well as the estimated variance-covariance matrix obtained from the Cox regression model fit. In particular the placebo adjusted version of MCPMod will be applied.

For the PoC testing and for the sample size calculation, the contrasts of each of the models to be tested must be pre-defined. The following cases has been selected to cover the plausible and a diverse range of potential dose response patterns.

Table 7.2.2: 1 Candidate case scenarios

	HR for each group vs Placebo in candidate cases*		
The response patterns	300 mg day1 150 mg q12w	600 mg day1 300 mg q12w	600 mg day1 300 mg q4w
Linear	0.64	0.41	0.10
E _{max} 1	0.17	0.13	0.10
E _{max} 2	0.11	0.10	0.10
Exponential	0.70	0.47	0.10

*The HRs are derived based on following models using planned total doses (i.e. the sum of all doses before Week 48): Linear; E_{max}1: assumes 70% of the maximum effect is achieved at low dose; E_{max}2: assumes 95% of the maximum effect is achieved at low dose; Exponential: assumes 35% of the maximum effect is achieved at medium dose. The scenarios in the table cover both the plausible and a diverse range of potential dose response patterns. For other HR combinations that is different but similar to the trend of the ones in the table, the primary analysis is robust and provide sufficient power. Hazard rates are rounded to two decimals.

The optimal contrasts corresponding to the candidate models are calculated and shown in Table 7.2.2: 2 (please note that no contrast for placebo is presented since placebo adjusted MCPMod test is applied). In the trial analysis stage, these optimal contrasts will be updated using the estimated variance-covariance matrix from the collected data (as suggested e.g. in [R15-4293]). The updated contrast coefficients will be described in the CTR.

Table 7.2.2: 2 Contrast coefficients

	Contrast coefficients for dose		
Model	300 mg day1 150 mg q12w	600 mg day1 300 mg q12w	600 mg day1 300 mg q4w
Linear	-0.177	-0.353	-0.919
E _{max} 1	-0.492	-0.579	-0.650
E _{max} 2	-0.565	-0.579	-0.588
Exponential	-0.146	-0.307	-0.940

A non-flat dose response is established if at least one contrast test (after adjusting for multiplicity using MCP step in MCPMod approach) is statistically significant, thereby rejecting the null hypothesis of a flat dose-response curve and indicating a benefit of BI 655130 over placebo. If a non-flat dose response is established, the statistically significant model(s) from the above candidate set are refitted to the data to generate new estimates for all model parameters.

If considered necessary and for the purpose of further model refinement, MCPMod might be repeated on the primary endpoint but with an extended set of shapes including the original candidates. Furthermore, covariates may be taken into account in further sensitivity analyses. Details of these analyses will be described in the TSAP.

Other analyses of the primary endpoint will include:

- Alternative PK metrics including model predicted metrics (e.g. cumulative AUC) for the dose regimens will be evaluated.

Secondary Objective: Formal Statistical Testing

Formal Statistical analysis

The primary analysis for the secondary objective on the time to first GPP flare up to week 48 for each dose of BI 655130 versus placebo will be tested using the stratified log-rank test stratified by the systemic concomitant use of GPP medications at randomization (yes or no) and based on the RS.

Kaplan-Meier (KM) estimates of the survival/failure probabilities at 1-monthly intervals, as well as the median time-to-event, will be provided by treatment. Confidence intervals will be based on two-sided $\alpha=0.05$. A Kaplan-Meier graph will also be produced.

If a patient discontinues the treatment early, the follow-up of the patient will be still continued and the primary analysis will include patients' on- and off-treatment data up to Week 48. If a patient has no GPP flare event through 48 weeks of study, or is lost to follow-up or withdrawn from the trial prior to achieving such an event, then the primary endpoint will be censored at the day of the last visit upon which it was confirmed that no GPP flare had yet been observed.

The primary method for handling of missing data on the time to first flare is described in [Section 7.3](#).

Secondary analysis of the primary endpoint will include:

- A sensitivity analysis utilizing the PPS to evaluate the impact on treatment outcomes of patients who may have relevant deviations from the conduct described in the CTP;
- Analysis of an additional estimand whereby for patients who used rescue medication or investigator-prescribed SoC prior to the first onset of a GPP flare is considered to indicate the onset of such a flare. For patients who use restricted medication for other disease and not for the onset of a GPP flare, data will be censored for further analysis following the use and imputed using the methods described in Section 7.3.
- Sensitivity analyses which utilize alternative methods for the handling of missing data as described in Section 7.3.
- Descriptive comparisons between the levels of each stratification (concomitant use of systemic GPP medications at randomization (yes or no)) and blocking factors (region (Japan or Rest of world) and population (adults versus adolescents)) will be performed.

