The acute phase is associated with a mean duration of hospitalization of 10 days (range 3-44 days) ([R16-0933](#)). Patients with GPP are known to be at an increased risk of death ([R16-3932](#)); ([R16-0581](#)). Six case series have published on deaths among patients with GPP ([R16-2698](#));([R16-1463](#)); (R16-0933); ([R17-3898](#));([R17-3456](#)); ([R17-3605](#)). Mortality estimates range from 2% in France (R16-2698) to 7% in Malaysia (R16-0933) and 7.7% in Thailand (R17-3456). In the US, Zelickson et al (R17-3605) conducted a case series on hospitalized patients with GPP at the Mayo clinic from 1961 to 1989 and reported a mortality rate of 3.2%. The most commonly reported causes of death in GPP patients were related to sepsis.

Mortality rates are also likely underestimated due to lack of identifying the cause of death as GPP and are largely driven by infectious complications and extra-cutaneous organ manifestations such as renal, hepatic, respiratory and cardiac failure (R16-0933). After responding to treatment or spontaneous flare cessation, it is estimated that up to 50% of patients may suffer from chronic GPP characterized by persistent erythema and scaling that may also include joint symptoms.

Moreover, in countries with lower incidence of GPP, the differential diagnosis can be delayed. This is partly due to the absence of a treatment protocol for GPP once it is diagnosed.

Based on the limitations described above, current therapeutic options are not suitable for life-long treatment and do not provide sustained responses in most patients. Therefore, there is a high need to develop (i) a highly effective treatment with rapid onset of action for patients presenting with an acute GPP flare; and (ii) to develop an effective treatment for prevention of the occurrence of flares that is safe and tolerable for lifelong treatment.

Role of IL-36R Signaling in GPP

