2.1.2 Primary endpoint(s)

The primary endpoint of the study is:

- Time to first Generalized Pustular Psoriasis (GPP) flare (defined by increase in Generalized Pustular Psoriasis Physician Global Assessment (GPPGA) score by ≥ 2 from baseline and the pustular component of GPPGA ≥ 2) up to week 48.

For the estimand concept on the above-defined primary endpoint definition, any use of rescue medication, or investigator-prescribed Standard of Care (SoC), will be considered to represent a GPP flare onset.

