3.3.2 Inclusion criteria

Each patient must meet all of the following inclusion criteria to be included into the trial:

1. Patients with a known and documented history of GPP per ERASPEN criteria (see [Section 3.3.1](#)) regardless of IL36RN mutation status, with at least 2 presentations of moderate to severe GPP flares with fresh pustulation (new appearance or worsening) in the past.
2. Patients with a GPPGA score of 0 or 1 at screening and randomization.
3. Patients who are not on concomitant GPP treatment at time of randomization (V2) must have had at least two presentations of moderate to severe GPP flare in the past year, at least one of which had evidence of either fever and/or elevated CRP and/or elevated WBC, and/or asthenia and/or myalgia.
4. Patients who are not on concomitant GPP treatment at time of randomization (V2) but who were on concomitant GPP treatment until shortly before randomization (V2) (≤ 12 weeks before randomization), these patients must have a history of flaring while on concomitant treatment for GPP or in case of dose reduction or discontinuation of their concomitant medication.
5. Patients who are on concomitant treatment regimen with retinoids and/or methotrexate and/or cyclosporine must stop at the day of randomization (V2). These patients must have

a history of flaring while on concomitant treatment for GPP or in case of dose reduction or discontinuation of these concomitant medications.

6. Male or female patients, aged 12 to 75 years at screening. For all patients, a minimum weight of 40 kg is required.
7. Signed and dated written informed consent and assent in accordance with ICH-GCP and local legislation prior to admission in the trial.
8. Women of childbearing potential (WOCBP)¹ must be ready and able to use highly effective methods of birth control per ICH M3 (R2) that result in a low failure rate of less than 1% per year when used consistently and correctly. A list of contraception methods meeting these criteria is provided in the CTP as well as in the patient, parent(s) (or patient's legal guardian) information.

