7.4 RANDOMISATION

If applicable, BI will arrange for the randomization and the packaging and labeling of trial medication. The randomization list will be generated using a validated system, which involves a pseudo-random number generator so that the resulting treatment will be both reproducible and non-predictable. Access to the codes will be controlled and documented.

Stratification for the concomitant use of systemic GPP medications at randomization (yes or no) will be done. If a patient received any GPP medication within 4 weeks prior to or at randomization, then this patient will be categorized as "yes" and otherwise, "no". Primary and key secondary efficacy analyses will be performed including an adjustment for this stratum.

Blocking for region (Japan versus Rest of World) will be done in order to ensure that sufficient patients per treatment group are recruited specifically to support individual country

submission in Japan; this factor will be treated as operational factor and will not be included into the analyses of efficacy endpoints.

Blocking for population (Adults versus Adolescents) will be done in order to ensure that there will be adolescent patients randomized in each treatment group for paediatric investigational plan; this factor will be treated as operational factor and will not be included into the analyses of efficacy endpoints.

The first twelve adolescent patients will be randomized in a 1:1:1:1 ratio to the four arms regardless of concomitant use of systemic GPP medications at randomization (yes vs. no) and blocking factor region (Japan vs. Rest of world). This is to ensure that within each randomized arm, there are at least 2 randomized adolescent patient. Any additional adolescent patients within each stratum (concomitant use of systemic GPP medications at randomization (yes vs. no) and each blocking factor region (Japan vs. Rest of world), will be randomized in a 1:1:1:1 ratio to the four arms.

The adult patients within each stratum (concomitant use of systemic GPP medications at randomization (yes vs. no) and each blocking factor region (Japan vs. Rest of world), will be randomized in a 1:1:1:1 ratio to the four arms.

The block size of the randomization will be documented in the CTR.

The process of randomization is done via an IRT. Practical aspects of the treatment allocation process are detailed in [Section 4.1.3](#).

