10. APPENDICES

10.1 INSTRUCTIONS FOR USE

10.1.1 Physician's Global Assessment for Generalized Pustular Psoriasis (GPPGA)

Erythema

- | | |
|--|--|
|  0 = Clear: | Normal or postinflammatory hyperpigmentation |
|  1 = Almost Clear: | Faint, diffuse pink or slight red |
|  2 = Mild: | Light red |
|  3 = Moderate: | Bright red |
|  4 = Severe: | Deep fiery red |

Pustules

- | | |
|--|---|
|  0 = Clear: | No visible pustules |
|  1 = Almost Clear: | Low density occasional small discrete (non coalescent) pustules |
|  2 = Mild: | Moderate density grouped discrete small pustules (non coalescent) |
|  3 = Moderate: | High density pustules with some coalescence |
|  4 = Severe: | Very high density pustules with pustular lakes |

[figure not shown]
Scaling/crusting

[figure not shown]
- | | |
|--|--|
|  0 = Clear: | No scaling and no crusting |
|  1 = Almost Clear: | Superficial focal scaling or crusting restricted to periphery of lesions |
|  2 = Mild: | Predominantly fine scaling or crusting |
|  3 = Moderate: | Moderate scaling or crusting covering most or all of lesions |
|  4 = Severe: | Severe scaling or crusting covering most or all lesions |

[figure not shown]
PGA Score for GPP

[figure not shown]
- 0 = If mean=0 for all three components
1 = If $0 < \text{mean} < 1.5$
2 = If $(1.5 \leq \text{mean} < 2.5)$
3 = If $2.5 \leq \text{mean} < 3.5$
4 = If $\text{mean} \geq 3.5$

[figure not shown]
Source: ([R15-5200](#))

[figure not shown]

[figure not shown]

[figure not shown]

[figure not shown]

[figure not shown]

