#### **Primary Objective: Dose Finding**

The Multiple Comparison Procedures and Modeling (MCP-Mod) approach ([19](#), [20](#)) is implemented in two main steps: (1) trial design stage; (2) trial analysis stage. The procedures for the trial design stage, including the selection of candidate models covering a suitable range of dose-response shapes and sample size and power calculations, are provided in the CTP Section 7.2.2. The procedures for the trial analysis stage are specified below.

For the primary analysis, the dose-response relationship will be modeled using the total planned dose. In this trial, the total is the sum of all planned randomized maintenance doses administered to the subject prior to week 48, including both loading and maintenance phase. Therefore, it is assumed that the cumulative concentration over time (AUC) and thus the cumulative total dose is the key driver of the efficacy response in the modeling part of MCP-Mod. [Table 7.4:1](#) shows the calculated total doses per treatment arm.

Table 7.4:1 Total dose per treatment arm during randomized maintenance treatment period

Treatment arm	Total dose
Speso SC Low: 300 mg day 1 150mg q12w	300mg at Day 1, 150mg at week 12, week 24 and week 36, Total dose:750 mg spesolimab
Speso SC Medium: 600 mg day 1 300mg q12w	600mg at Day 1, 300mg at week 12, week 24 and week 36, Total dose:1500 mg spesolimab
Speso SC High: 600 mg day 1 300mg q4w	600mg at Day 1, 300mg at week 4, week 8, week 12, week 36, week 20, week 24, week 28, w32, w36, week 40, week 44 Total dose: 3900 mg spesolimab
Placebo	Placebo at Day 1, week 4, week 8, week 12, week 16, week 20, week 24, week 28, w32, w36, week 40, week 44, Total dose 0 mg spesolimab

The responses for treatment difference estimate over placebo for each active dose group, which is based on the log hazard ratio of the active doses versus placebo, as well as their estimated variance-covariance matrix estimate for the primary endpoint are estimated by stratified Cox regression model on the time to the first GPP flare. The subsequent MCP-Mod analysis are based on the log hazard ratio from the stratified Cox regression model. In the case

of zero event in one/some of the arms by stratum, the stratified Cox regression model will be conducted using Firth's penalization ([21](#), [22](#), [23](#))

*Sample code*

```
PROC PHREG DATA=adtte;  
CLASS treatment stratification (REF='placebo');  
MODEL aval*cnsr (list)=treatment/ TIES=BRESLOW FIRTH;  

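### Baseline GPPGA (0 or 1) sets the score a flare requires but is not in the Cox model behind MCPMod and the reported hazard ratios; one covariate would be an optional, low-cost guard against chance imbalance.

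*Protocol*

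**What the plan says.** - **Endpoint.** CTP 2.1.2 defines the primary endpoint as "Time to first Generalized Pustular Psoriasis (GPP) flare (defined by increase in Generalized Pustular Psoriasis Physician Global Assessment (GPPGA) score by" 2 or more from baseline, with a pustular component of 2 or more). Rescue medication or investigator-prescribed standard of care (SoC) also counts as a flare.
- **Entry.** CTP 3.3.2 admits "Patients with a GPPGA score of 0 or 1 at screening and randomization".
- **Scoring.** In CTP 10.1.1 the GPPGA comes from the mean of three components, each scored 0 to 4. Score 0 applies "If mean=0 for all three components"; score 2 starts at a mean of 1.5 and score 3 at 2.5.
- **Randomisation.** CTP 7.4 stratifies by systemic GPP medication and blocks by region and by adult or adolescent. Of the medication factor it says "Primary and key secondary efficacy analyses will be performed including an adjustment for this stratum". Baseline GPPGA is not used.
- **Model.** In CTP 7.2.2 each "hazard function for patient i in stratum m (systemic concomitant use of GPP medications at randomization (yes or no)) is assumed to have the form" of a baseline hazard for the stratum multiplied by an exponential in three treatment indicators. The SAP code (7.4.1) has treatment alone, "MODEL aval*cnsr (list)=treatment/ TIES=BRESLOW FIRTH", within medication strata. SAP 7.4.1 takes the hazard ratios shown for the secondary objective from the same model.
- **Covariates.** CTP 7.2.2 allows that "covariates may be taken into account in further sensitivity analyses", and names none.

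**The concern.** Baseline GPPGA is part of the event definition, because it fixes the absolute score that counts as a flare. That makes it a natural candidate for adjustment. Both levels are likely to be present: CTP 1.1 says that after a flare "it is estimated that up to 50% of patients may suffer from chronic GPP characterized by persistent erythema and scaling", although this does not fix the split in this trial.

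Randomisation protects the test on average, but it does not balance 30-patient arms in any one trial. If flare risk differs by baseline level, an uneven split moves the log hazard ratios that feed the dose-response test, the fitted curve and the reported hazard ratios. The move can go in either direction. What is at stake is robustness to that imbalance. Neither validity nor precision is at issue.

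**Working it through.** **1. Thresholds (CTP 10.1.1).** GPPGA 2 needs a component sum of at least 3 × 1.5 = 4.5, so 5 of 12. GPPGA 3 needs at least 3 × 2.5 = 7.5, so 8 of 12. Baseline 0 means a sum of 0; baseline 1 means a sum of 1 to 4. The required rise in component points is 5 from baseline 0 and 8 − 4 = 4 to 8 − 1 = 7 from baseline 1, so the two overlap.

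**2. Reproducing the plan's figures (CTP 7.5).** Expected events per arm are 30 × {1 − exp[−(3a + 8.04b)]}, where a and b are the monthly rates before and after 3 months, and 48 weeks is 11.04 months.

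- Placebo, Base: 3 × 0.171 + 8.04 × 0.03 = 0.754, giving 15.9 events.
- High, medium and low dose: 2.2, 3.1 and 6.1.
- Total: 27.2 by rounding the sum (target 27; table 2, 3, 6 and 16).

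Simulated MCPMod success was 99.5% in Base (stated 99.5%) and 90.2% in BaseMinus (stated 90.7%). There were 10,000 trials per case with 30 per arm. The Cox model was stratified by medication, and the four candidate shapes were used with contrasts updated from the estimated covariance, at one-sided 0.05. Firth penalisation was used throughout because 73-75% of simulated trials had an arm-by-stratum cell with no event, which is the SAP's trigger for it.

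**3. Assumptions not in the documents.** These are the share of patients at each baseline level; a nil, twofold or threefold hazard ratio between levels; and a medication stratum split 50/50 with no effect of its own. Hazards were scaled so that each arm's average matches the protocol.

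**4. Chance imbalance.** With X ~ Binomial(30, p) in each arm, a gap of 20 points is 6 patients. For one active arm the probability is P(|X_active − X_placebo| ≥ 6). For at least one of three arms sharing one placebo arm it is Σ P(X_placebo = x)·[1 − P(|X_active − x| < 6)³].

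| Share at one level | A given active arm | At least one of three |
|---|---|---|
| 10% | 1.8% | 4.7% |
| 20% | 7.5% | 18.1% |
| 30% | 12.0% | 27.8% |
| 50% | 15.5% | 34.8% |

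For a given arm, half of these gaps go each way.

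**5. Shift from a 20-point gap.** Factor on the hazard ratio = exp(0.2 × slope), where the slope is that of the estimated log hazard ratio on the arm-minus-placebo share.

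- Twofold effect, 50/50: slopes 0.64-0.75, factors 1.14-1.16 (about 0.2 SD).
- Threefold effect, 50/50: slopes 0.91-1.07, factors 1.20-1.24 (about 0.27 SD).
- Shares of 10-90%, unadjusted: 1.08-1.19 (twofold) and 1.17-1.34 (threefold).
- With the covariate, all cases: slopes −0.23 to +0.13, factors 0.95-1.03.

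The SD of the high-dose log hazard ratio is about 0.74. Imbalance explains 0.3-1.7% of its variance (twofold) or 0.7-3.2% (threefold).

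**6. Success probability, unadjusted to adjusted.** BaseMinus at 50/50: 90.2 to 90.1% (nil), 89.0 to 90.0% (twofold), 86.8 to 88.8% (threefold). The BaseMinus gain in points, by share of the higher-risk level (paired SE 0.11-0.24), was:

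| Share | 10% | 20% | 30% | 50% | 70% | 80% | 90% |
|---|---|---|---|---|---|---|---|
| Twofold | +0.4 | +0.8 | +0.6 | +0.9 | +0.4 | +0.3 | +0.2 |
| Threefold | +1.2 | +2.4 | +2.5 | +2.0 | +1.3 | +0.9 | +0.2 |

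In Base the change was −0.04 (nil), +0.1 (twofold) and +0.1 to +0.4 (threefold) points. Rejection under no effect was 3.8-4.4% unadjusted and 3.9-4.7% adjusted, against a nominal 5%.

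A second simulation without strata (5,000 paired runs per setting, hazard ratio between levels 0.33 to 3) gave changes of −0.1 to +0.4 points in Base and −0.2 to +2.3 in BaseMinus. Size there was 3.5-4.2% unadjusted and 3.5-4.4% adjusted.

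**7. Cost in precision.** The SD of the high-dose log hazard ratio rose from 0.734 to 0.740 with a nil effect at 50/50, about 1%, and by 0.3-3.0% over the cases run.

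**The case against.** The strongest reply is that there is no defect here, only a preference for another model. The plan stratifies on medication use, and CTP 7.5 gives the reason such use matters: withdrawal may trigger flares. With about 27 events a sparse model is defensible. That stands, and it is why the change is optional.

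The benefit also rests wholly on assumed inputs. Baseline 1 needs a higher score to flare but may reflect residual disease, so the two could offset. The component rises overlap, and SoC use counts as a flare without the threshold. A nil effect is credible, and any link between medication use and residual disease was not simulated. All of this stands. A reader might infer that baseline-1 patients must flare less often, but the documents give no direction.

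A further reply is that the plan already permits covariates. CTP 7.2.2 does, but optionally, unnamed and only in sensitivity analyses. A reader might conclude that no adjusted analysis is planned. That cannot be said, because redacted SAP sections may contain one. What can be read is that the primary model omits the term.

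Finally, it would be too strong to say that the covariate removes the whole shift. The adjusted and unadjusted ranges are not paired case by case, and adjusted slopes reach −0.23.

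**Conclusion.** The point holds as an optional improvement. Baseline GPPGA determines whether a flare requires GPPGA 2 or 3, and it appears in neither the randomisation nor the Cox model that feeds MCPMod and the reported hazard ratios.

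A reader might infer that the omission invalidates the dose-response test or undermines the sample size. The documents and the calculations do not support that: rejection under no effect stays below 5%, and Base success stays at about 99.5%.

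If baseline GPPGA is prognostic, imbalances with a probability of about 5-35% can shift the log hazard ratios modestly, by amounts small beside sampling error. Adjustment largely removes the shift, though complete removal is not shown. It changes BaseMinus success by about 0 to +2.5 points, the top of that range needing a threefold effect, and by about 0 if baseline GPPGA is not prognostic. Confidence is medium, because the split and the prognostic effect are both assumed.

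**What to change.** Before unblinding, prespecify baseline GPPGA (0 versus 1) as one covariate, not a stratum, in the medication-stratified Cox model of CTP 7.2.2 and SAP 7.4.1. Keep Firth penalisation as the SAP provides, and keep the unadjusted model as a sensitivity analysis. Name baseline GPPGA in the by-arm baseline table already planned in SAP 7.1. Leave the stratified log-rank test unchanged.

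No new data are needed. The costs are:

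- The hazard ratio becomes conditional on baseline GPPGA. Because the SAP ties the secondary-objective hazard ratio to the same model, it no longer matches the medication-only log-rank test exactly.
- One more term is estimated from about 27 events (Base) or 23 (BaseMinus).
- The SD increase in step 7 of the working is accepted.
- Protocol and SAP wording must both be amended, and under CTP 8.1 protocol amendments need ethics committee and authority approval.

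If the sponsor prefers to keep the primary model, a lesser step is to name baseline GPPGA before unblinding in the covariate sensitivity analysis that CTP 7.2.2 already allows. That prespecifies the check but leaves the main dose-response analysis unadjusted.
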